The BAS3 number skills achievement subscale is designed for adaptive testing: children start the test at a level considered appropriate for their age and are presented with easier items if they do not meet a criterion for moving to more difficult items; or are presented with progressively more difficult items until they can no longer meet the criterion for moving forward. The number skills scale has 51 items grouped into blocks of six items and one nine-item block. The suggested starting point for children in this trial given their ages (seven to eight years old) is item seven. Every child takes all items within a block and the next easiest block is administered until the child passes four or more items. Total scores are calculated by summing the number of questions answered correctly by pupils. Correct answers receive one point, while incorrect answers or no answers are scored as zero (Elliot & Smith, 2011). Given that this is a commercial test, it is not included in the appendix of the SAP.

Pilot testing was undertaken in Phase 1 to understand the extent to which scores of low attaining pupils were normally distributed. Details on this are presented in Appendix A.

Given the adaptive nature of the BAS3 number skills subscale, in this trial we use the age-standardised score in the primary outcome model.³ This age-standardised score is a more useful measure than the raw or ability scores also available for the subscale, as the age-standardised score makes an allowance for the different ages of the pupils and can be compared against nationally representative samples, i.e., can easily identify if pupils score below or above the national average. The age standardised score for BAS3 ranges from 55 to 145.

Secondary outcome measures

Three secondary outcomes will be captured as part of this trial in addition to the primary outcome:

- 1) **Wider maths attainment** based on the Progress Test in Maths (PtM) (Level 8, GL Assessments)
- 2) **Working memory** based on the Working Memory Battery (WMB) (for Children Listening Recall, Counting Recall, Backward Digit Recall subtests (Pickering & Gathercole, 2001))
- 3) **Attention and behaviour** as measured by the SNAP-IV Teacher Attention Rating Scale.

These are outlined further below.

1) Wider maths attainment

³ It is unclear which BAS3 score was used in the efficacy trial. Based on the pilot we have decided to use the age-standardised scores.

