Although the intervention is designed to impact pupils' number skills rather than their wider mathematics attainment, in order to explore the impact of IWM+A on maths attainment in general, a wider measure of maths attainment will be used to analyse if IWM+A supports maths learning more generally. Wider maths attainment will be measured using [GL Assessment's Progress Test in Mathematics](#) (PTM). GL PTM was selected as the wider maths attainment measure because it is widely used by schools and it is well aligned to the national mathematics curriculum. PTM has been standardised on a sample of British children from diverse school level country, independent/grammar schools and previous attainment (Swinson, 2013). The measure adequately measures generic maths skills and reports for the same indicate good face validity, and excellent internal consistency.

In consultation with GL it was decided that Version 8, designed to be used by Year 3 children in the spring/summer term, would be used despite the lower ability level of the pupils. It was felt that Version 8 was the most appropriate and that the underlying constructs and the range of items available would mitigate against potential floor effects. The test takes approximately 60 minutes.

The group-delivered test will be administered to all ten selected pupils in each school at the same time under exam conditions by independent test administrators from AlphaPlus who will be blinded to allocation status. Tests will be marked by GL markers who will not know school allocation, thus adding an extra layer of blinding. EYFSP will be used as a baseline.

Despite the fact that the age-standardised score allows for benchmarking against national levels and trends, for this analysis the raw score will be used, to mitigate against prior instances of floor effects when used with lower-attaining pupils (Hodgen et al., 2019). Further details on the analysis plans are outlined in the Secondary Outcome analysis section.

2) Working memory

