The effect size (Hedge's g) will be calculated for τ . The effect size will be standardised using unconditional variance in the denominator and confidence intervals will be reported to communicate statistical uncertainty in line with EEF guidance (see EEF 2018). This will tell us the average effect of the intervention on pupil outcomes in treatment schools compared to those in control schools.

All analyses will be run in Stata, versions 17 onwards.

Secondary outcome analysis

This effectiveness trial has three secondary outcome measures: wider math attainment; working memory; and attention and behaviour.

The secondary outcome analysis will follow the same procedures and use Equation (1) to estimate each respective secondary outcome model, as described in the primary analysis, substituting the primary outcome variable in turn with each of the secondary outcome variables.

For the secondary outcome analysis for Wider Maths and for Working Memory, the X_{ij} vector for pupil i in school j will be represented by the EYFSP score as the baseline. Whilst neither Wider Maths scores nor Working Memory are age-standardised, in the main analysis we will not include age in the pupil-level characteristics, X_{ij} , as the trial is within one year group, somewhat minimising concerns over age effects. If we expect Wider Maths or Working Memory scores to be age-correlated, this may introduce bias into the measurement of τ .⁵ As an additional sensitivity analysis, we will run the regressions with age (in months) included as a covariate in X_{ij} . We will also run a sensitivity analysis on the inclusion of EYFSP: given this was collected at the end of reception, it is possible that the correlation between EYFSP and current attainment is weaker than expected for a baseline measure, and may be introducing additional noise. For the secondary outcome analysis for Attention and Behaviour, the associated baseline measure will be used, since SNAP-IV has been administered at baseline.

Subgroup analyses

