⁵ Due to randomisation, bias will only be introduced in τ if age is correlated with effectiveness of the IWM+A treatment (that is if older pupils improve more rapidly in response to the intervention). Whilst generally any omitted variable would introduce bias in all coefficient estimates, bias will not be introduced if the included variable is both uncorrelated with the omitted variable and all other covariates. By virtue of randomisation, treatment assignment should not be correlated with either school-level characteristics, Z_{ij} , or pupil-level characteristics (including age), X_{ij} . Thus the only reason τ would be biased would be if the treatment effect is correlated with age.

⁶ NPD Alias for this variable is: EVERFSM_6_P_[term][yy]. The variable indicates whether the pupil 'has ever been recorded as eligible for free school meals on Census day in any termly or annual Census (including Alternative Provision Census and PRU Census where available) in the last 6 years up to the pupil's current year (not including nursery)'.

The protocol also outlines an additional compliance analysis. This is outlined below (see [Compliance](#)).

Longitudinal follow-up analyses

Longitudinal analysis will be commissioned separately to this trial.

Balance at baseline

A well-conducted randomisation should create groups that are equivalent at baseline, with any imbalance at baseline occurring by chance (Glennerster & Takavarasha, 2013). However, to check for, and monitor, imbalance at baseline in the realised randomisation, baseline equivalence testing will be conducted at the school and pupil level.

At the school level, we will check the balance in the following variables by means of cross-tabulations and histograms that assess the distribution of each characteristic between the control and intervention groups. We will also report associated effect sizes to quantify the magnitude of any observed imbalance (for continuous measures), but will not undertake statistical testing as the initial randomisation necessarily means that any imbalance we observe is due to chance and therefore statistical tests are not appropriate:

- Ofsted ratings;
- Proportion of children eligible for FSM.⁷

At the pupil level, balance will be assessed as above but for the following characteristics:

- Gender;
- Age (in months);
- Prior attainment using the EYFSP;
- SNAP-IV Teacher Attention Rating Scale;
- FSM status for pupils.

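### The main Wider Maths and Working Memory models omit age at a small cost in precision, and the accompanying caveat wrongly treats the omission as a possible source of bias

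*SAP*

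**What the plan says.** Under Secondary outcome analysis, the SAP reuses Equation (1) for Wider Maths and Working Memory with EYFSP as the pupil-level baseline and region as the stratum term. On age:

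- It acknowledges that neither score is age-standardised, yet "in the main analysis we will not include age in the pupil-level characteristics".
- The reason is the narrow age range: "as the trial is within one year group, somewhat minimising concerns over age effects".
- A caveat follows: "If we expect Wider Maths or Working Memory scores to be age-correlated, this may introduce bias into the measurement of" τ.
- Footnote 5, attached to that caveat, argues from randomisation and concludes: "Thus the only reason τ would be biased would be if the treatment effect is correlated with age".
- The text then plans a check: "As an additional sensitivity analysis, we will run the regressions with age (in months) included as a covariate".

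Under Secondary outcome measures, the SAP says of the maths test that "for this analysis the raw score will be used", to guard against floor effects in low attainers. Working Memory is a factor score built from subtest totals. For the primary outcome, by contrast, one reason given for the chosen score is that "the age-standardised score makes an allowance for the different ages of the pupils". Table 4 reports age for 1,004 of 1,004 control pupils and 990 of 992 intervention pupils.

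**The concern.** There are two separate matters.

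The first is the choice of main model. Both scores carry whatever age gradient exists within Year 3, and the main models leave it in the residual. Age is fixed before randomisation, almost complete and already in the dataset. The existing pupil-level covariate is weak by the SAP's own account: EYFSP dates from Reception, has a restricted range, and its assumed correlation of 0.5 is described as probably too high. Working Memory has no baseline of its own.

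The second is the reasoning. The main text says that correlation of the score with age may bias τ. Footnote 5 says that this is not enough and that the treatment effect must vary with age. These are different conditions, and neither biases the average effect in a randomised comparison. The sensitivity analysis adds age only as a main effect, so it could not detect or remove the age-by-treatment interaction that the footnote names as the sole problem. A reader who follows the footnote could take a gap between the two estimates as a sign of bias or effect modification, when it would mainly reflect chance imbalance and precision.

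**Working it through.** **1. The bias statement.** Let the effect for a pupil of age a be τ + δ(a − ā), where ā is the mean age of the trial population. Averaged over pupils, the second term is zero, so the average effect is τ. Randomisation makes age independent of arm in expectation, so a comparison without age has expectation τ whether or not δ = 0, and whether or not age predicts the score.

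A simulation agrees. It used 4,000 trials of 201 schools with 10 pupils each, ICC 0.16, a within-school age–score correlation of 0.3, and an effect of 0.20 on average that rises by 0.10 per SD of age.

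- Without age: mean estimate 0.201 (Monte Carlo SE 0.001), SD 0.0718.
- With age as a main effect: mean estimate 0.201, SD 0.0700, about 2.5% smaller.

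So there is no bias in either model, and a small gain in precision from adjustment.

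**2. Reproducing the SAP's MDES.** Inputs from Table 3 and the power section: J = 201 schools, n = 1,996/201 = 9.93 pupils per school, ICC 0.16, two-sided alpha 0.05, power 0.80, P = 0.5, pupil-level R² = 0.25 (or 0), school-level R² = 0.

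MDES = M × √[ICC/(P(1−P)J) + (1−ICC)(1−R²)/(P(1−P)Jn)], where M = t(0.975) + t(0.80) on 199 df ≈ 2.815.

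- School term: 0.16/50.25 = 0.003184.
- Pupil term at R² = 0.25: 0.84 × 0.75/(50.25 × 9.93) = 0.001263.
- MDES = 2.815 × √0.004447 = 0.1877. The SAP gives 0.188.
- At R² = 0 the result is 0.1964 (0.1962 with n = 10). The SAP gives 0.196.

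The school term is 0.003184/0.004447 = 72% of the variance, and a pupil-level covariate does not reduce it.

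**3. Adding age.** The SAP gives no correlation between age and these scores, so r = 0.1 to 0.4 is assumed. Age is taken to explain r² of the pupil-level variance left after EYFSP: R² becomes 0.25 + 0.75r², or r² if EYFSP explains nothing.

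| Assumed r | MDES, EYFSP r = 0.5 (0.1877 without age) | MDES, EYFSP r = 0 (0.1964 without age) |
|---|---|---|
| 0.1 | 0.1875 (−0.1%) | 0.1961 (−0.2%) |
| 0.2 | 0.1867 (−0.6%) | 0.1951 (−0.7%) |
| 0.3 | 0.1853 (−1.3%) | 0.1933 (−1.6%) |
| 0.4 | 0.1834 (−2.3%) | 0.1909 (−2.8%) |

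In the first column, power at the current MDES rises from 0.80 to between 0.801 and 0.818. If age also explained the same share of between-school variance, 0.1877 would fall to between 0.1868 and 0.1721, but nothing in the SAP supports that assumption.

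**4. The chance age difference.** Table 4 gives means of 90.4 (SD 3.8) and 90.2 (SD 3.7) months, so the intervention arm is 0.2 months younger: 0.2/3.75 = 0.053 SD. Multiplied by r = 0.1 to 0.4, this is 0.005 to 0.021 SD against the intervention if scores rise with age.

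**5. The year-group reason.** A uniform spread over 12 months has SD 12/√12 = 3.46 months. The observed SDs of 3.8 and 3.7 show that the sample covers at least a full year of age, so the restriction to Year 3 leaves the ordinary within-year spread intact.

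**The case against.** The strongest reply is that little turns on this. The age-adjusted model is prespecified, so both estimates will be reported, and the proposal mostly swaps which is labelled main. The gain in precision is at most 2.3% of the MDES under the planned assumptions and could be near zero. Selecting the ten lowest attainers in each school may also weaken the association between age and score. A shift of 0.005 to 0.02 SD is far below the MDES, and the standard error already allows for chance differences of this kind. All of that stands, and it makes the point minor. It is not an argument for leaving age out, because adjustment costs one degree of freedom.

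Three stronger readings are tempting, and the SAP does not support them:

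- A reader might infer that age was dropped because of the mistaken bias argument. The stated reason is the single year group. The bias remark is a caveat that leads towards the age-adjusted run.
- A reader might infer that the plan treats its outcomes inconsistently without explanation. It explains the raw maths score by floor effects, and the age-standardised BAS3 score also by the adaptive test and national benchmarking. Floor effects are a reason for the raw score, however, and not for omitting age from its model.
- A reader might infer that the two secondary estimates will be biased. They will not.

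**Conclusion.** A minor point that holds. The caveat in Secondary outcome analysis and the conclusion of footnote 5 are statistically wrong, and the planned main-effect adjustment would not address the interaction that the footnote names. Omitting age gives up a little precision: the MDES would fall by about 0.1% to 2.3% with EYFSP r = 0.5, or 0.2% to 2.8% with r = 0. It also leaves unadjusted a chance difference worth about 0.005 to 0.02 SD.

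The error in reasoning needs no numerical assumption. The sizes rest on assumed age–score correlations of 0.1 to 0.4, on applying the efficacy trial's ICC of 0.16 to these two outcomes, and on age explaining pupil-level variance only. No material loss of power is shown.

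**What to change.** - For Wider Maths and Working Memory, include age in months in the pupil-level covariates of the main model, and keep the model without age as the sensitivity analysis.
- Replace the bias sentence and the end of footnote 5 with a statement that, under randomisation, omitting age affects precision and the handling of chance imbalance, and does not bias the average effect.
- State how the two pupils without an age are handled, for example by setting them to the mean age.
- If variation of the effect with age is of interest, add an age-by-treatment term labelled exploratory.

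The cost is SAP wording and one degree of freedom per model. Both models are already planned and no new data are needed. The change should be made before endline data are analysed, because promoting the adjusted model afterwards could look driven by the results.

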Outcome measures section for more detail on the BAS3 and EYSFP). The pupil level BAS3 scores will be age-standardised with a mean of 100 and standard deviation of 15.

To address the primary research question an intention-to-treat (ITT) analysis will be undertaken using multi-level modelling (MLM) with fixed effects and random intercept. In ITT, data is analysed according to the group randomised, regardless of whether the treatment was actually received as intended, and irrespective of withdrawal from the intervention post-randomisation, or deviations in programme implementation. This principle is key in ensuring an unbiased analysis of intervention effects and is in line with the EEF's guidance (see EEF 2018).

To account for the nested nature of the data, a hierarchical linear model with two levels (school, pupil) will be fitted controlling for pre-intervention scores at the pupil level. Following the stratified randomisation, the model will include a term identifying the regions (strata).

Impact will be estimated by fitting the model in equation (1). Equation (1) is known as a 'random intercepts' model because $\beta_{0j} = \beta_0 + u_j$ is interpreted as the school-specific intercept for school j and $\beta_{0j} \sim i.i.d. N(\beta_0, \sigma_u^2)$ is random (it is a number that can take any value):

$$(1) \quad Y_{ij} = \beta_0 + IWMA_j \tau + Z_j \beta_1 + X_{ij} \beta_2 + u_j + e_{ij}$$

Where:

Y_{ij} = BAS3 scores on the number skills subtest for child i in school j ;

β_0 = the cluster-level coefficient for the slope of a predictor on number skills;

$IWMA_j$ = a binary indicator of the school assignment to intervention [1] or control [0];

Z_j = school-level characteristics i.e. the stratifying variable of geographical location (as used for randomisation);

X_{ij} = pupil level characteristics for pupil i in school j , i.e. the pre-intervention EYFSP score;

u_j = school-level residuals and

e_{ij} = individual-level residuals.

The coefficient τ in Equation 1 above will represent the outcome of the trial, with respect to the primary outcome measure. Equation 1 will also be replicated for each of the three secondary outcome measures (see next section).

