As defined in the trial protocol, we will conduct a subgroup analysis for pupils eligible for FSM, using the same model as our primary analysis (Equation 1). With this analysis we will explore differential effects of IWM+A for FSM pupils as they are considered a key target group by the EEF. We will identify FSM pupils within the sample of intervention and control schools as they are registered in the NPD, using the variable EVERFSM_6_P.⁶ Analysis will be undertaken using a binary FSM variable where FSM-eligible=1; non-FSM-eligible=0.

The study will first report mean outcomes by sub-categories of FSM-eligible children as a basic descriptive step. Then, we will enter an interaction term in Equation (1) above, to account for the FSM subgroup and treatment allocation while retaining the whole analytical sample in the model.

For the subgroup analysis, effect sizes and statistical uncertainty will be calculated and communicated as per the primary analysis (also see section on Effect size calculation).

Additional analyses

In the protocol we suggested we would use factor analysis to understand the extent to which specific factors in PtM linked to IWM+A are impacted by the intervention. However, on reflection we believe the most appropriate and robust use of the data is to use same analytical model as the primary analysis. We believe this is correct for two reasons. Firstly, the BAS3 Number Skills subscale has been developed specifically to measure number skills and it is a reliable measure of this concept, in contrast our factor scores from the PtM would be exploratory as the PtM has not been used in this way widely. Secondly, interpretation of the same concept using two different measures feels unnecessary – especially given potential issues already discussed. For these reasons we think that we should prioritise the BAS3 as our primary outcome measure and use the PtM as a secondary outcome measure focusing on wider maths attainment.

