The ICC is a key parameter for clustered trials. It represents the proportion of variance in a given outcome that can be explained by the variation between clusters (i.e. schools) as opposed to within-clusters.

The ICC used for the power calculations reported in the section on Sample size and power calculations overview and at protocol stage (see the [IWM+A evaluation protocol](#) for more information) is based on the ICC reported at analysis stage in the [previous EEF IWM efficacy trial](#), at 0.16.

In the final report we will report ICCs as at protocol stage; as at randomisation; and at analysis stage. The ICC at analysis stage will be based on the primary outcome measure; and will be calculated using: (i) the same model as Equation (1) and; (ii) a model similar to that documented in Equation (1) but with no covariates, accounting for the clustering of pupils in schools (the so-called empty model). ICCs will be estimated using Stata's `estat icc` command.

Effect size calculation

We will use the effect sizes (hereafter ES) for cluster-randomised trials given in the EEF evaluator guidance, as adapted from Hedges (2007):

$$ES = \frac{(\bar{Y}_T - \bar{Y}_C)_{adjusted}}{\sqrt{\sigma_S^2 + \sigma_{error}^2}}$$

Where $(\bar{Y}_T - \bar{Y}_C)_{adjusted}$ is the mean difference between the intervention and control group adjusted for baseline characteristics and $\sqrt{\sigma_S^2 + \sigma_{error}^2}$ is an estimate of the population standard deviation (variance).

From the primary outcome model, we will take each group's adjusted mean and variance to calculate the effect size. This variance will be the total variance (across both pupil and school levels, without any covariates, as emerging from a 'null' or 'empty' multi-level model with no predictors). The ES therefore represents the proportion of the population standard deviation attributable to the intervention (Hutchinson & Styles, 2010). A 95% CI for the ES, that takes into account the clustering of pupils in schools, will also be reported. Effect sizes will be calculated for each of the models estimated.

All ES will be estimated using the `eefanalytics` Stata package.¹³

¹³ See here for more information <https://ideas.repec.org/c/boc/bocode/s458904.html>

References

- Allison, P. D. (2012). Handling missing data by maximum likelihood. *SAS global forum*, 2012 (312), 1038-21.

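### The arm-by-FSM interaction is tested with a school random intercept only, so its interval is too narrow if the FSM gap varies between schools

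*SAP*

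**What the plan says.** Under Primary outcome analysis, the SAP specifies "multi-level modelling (MLM) with fixed effects and random intercept" and describes it as follows: "a hierarchical linear model with two levels (school, pupil) will be fitted controlling for pre-intervention scores at the pupil level". Equation (1) has one school residual and one pupil residual, and the text names it accordingly: "Equation (1) is known as a 'random intercepts' model".

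Under Subgroup analyses, the same model is used for FSM. The plan states that "we will enter an interaction term in Equation (1) above, to account for the FSM subgroup and treatment allocation", and that this is done "while retaining the whole analytical sample in the model". On precision it says: "For the subgroup analysis, effect sizes and statistical uncertainty will be calculated and communicated as per the primary analysis". The Effect size calculation section adds: "A 95% CI for the ES, that takes into account the clustering of pupils in schools, will also be reported". It assigns all effect sizes to the `eefanalytics` Stata package.

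The SAP mentions no school-level random FSM coefficient, no cluster-robust variance and no sensitivity check for this model.

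**The concern.** Arm by FSM is a cross-level interaction. Its sampling error depends partly on how far the difference between FSM and non-FSM pupils varies from school to school. A single school intercept moves both groups by the same amount, so the model takes the gap as identical everywhere and treats any real variation as independent pupil noise. The random intercept protects the standard error of the overall treatment effect, but not that of the interaction.

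The SAP makes FSM pupils a key target group and presents the trial as powered for them. A claim that the programme works differently for FSM pupils would rest on this interaction. Some variation in the gap is plausible, since each intervention school delivers through one nominated TA, but that is an inference and not a documented figure.

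**Working it through.** **Inputs from the SAP.** 201 schools (100 intervention, 101 control), about 10 pupils each; ICC 0.16 in both the overall and FSM columns of Table 3; pupil-level R² 0.25; 804 FSM pupils (40.3%); 189 schools with at least one FSM pupil, so 12 with none; two-sided alpha 5%.

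**The plan's own figures first.** With df = J − 3, MDES = (t₀.₉₇₅ + t₀.₈₀) × √[ICC/(0.25 J) + (1 − ICC)(1 − R²)/(0.25 J n)].
- Overall, J = 201, n = 10: 2.815 × √(0.003184 + 0.001254) = 0.188, as stated.
- FSM, J = 189, n = 4: 2.817 × √(0.003386 + 0.003333) = 0.231, as stated.

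The FSM figure is a calculation for FSM pupils alone. It does not describe the whole-sample interaction model.

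**Assumptions.** On a total outcome variance of 1, the school intercept variance is 0.16 (SD 0.4) and the pupil residual variance is 0.84 × 0.75 = 0.63. FSM counts per school are beta-binomial with mean 40.3%, fitted so that the chance of no FSM pupil is 12/201. The between-school SD of the FSM gap, s, is not in the SAP and is set to 0.1, 0.2 and 0.3. Its correlation with the intercept, r, is also not in the SAP and is varied.

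**Method.** For pupils i and k in one school, with F = 1 for FSM, the true covariance V has school part 0.16 + r(0.4)s(Fᵢ + Fₖ) + s²FᵢFₖ, plus 0.63 on the diagonal. The random-intercept model fits W = a·11ᵀ + b·I, with a and b taken at the values to which maximum likelihood converges. With A = ΣXᵀW⁻¹X and B = ΣXᵀW⁻¹VW⁻¹X, the reported variance is A⁻¹ and the true variance is A⁻¹BA⁻¹. Error of a nominal 5% test is 2Φ(−1.96 × reported SE / true SE).

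Example for the interaction at s = 0.2, r = 0: a = 0.168, b = 0.638, reported SE 0.080, true SE 0.085, ratio 1.062, error 2Φ(−1.96/1.062) = 6.5%.

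| Gap SD s | Interaction, r = 0: true/reported SE | Error | FSM effect, r = 0: true/reported SE | Error |
|---|---|---|---|---|
| 0.1 | 1.02 | 5.4% | 1.01 | 5.3% |
| 0.2 | 1.06 | 6.5% | 1.05 | 6.3% |
| 0.3 | 1.13 | 8.4% | 1.11 | 7.8% |

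**Sensitivity to r.** The interaction result hardly moves: at s = 0.2 its error is 6.3% at r = −0.5 and 6.6% at r = +0.5. The FSM effect does move: at s = 0.2 its error runs from 4.4% to 7.8% over the same range.

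**The value of r that matches Table 3.** School variance among FSM pupils is 0.16 + s² + 0.8rs. At r = 0 this is 0.17, 0.20 and 0.25. With the unadjusted pupil variance of 0.84, the FSM ICC is then 0.17/1.01 = 0.168, 0.20/1.04 = 0.192 and 0.25/1.09 = 0.229, not 0.16. Holding it at 0.16 needs s² + 0.8rs = 0, so r = −s/0.8 = −0.125, −0.25 and −0.375. At those values the FSM-effect ratio is 1.004, 1.016 and 1.037, with error 5.1%, 5.4% and 5.9%.

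**Simulation.** Refitting the random-intercept model by REML (2,000 runs per setting, r = 0) gave interaction error of 4.5%, 6.9% and 9.2% at s = 0, 0.2 and 0.3. A separate set of 1,500 runs per setting compared model-based with school-clustered robust errors: 6.4% v 5.2% at s = 0.2, 8.3% v 4.2% at s = 0.3, and 5.1% for both with no gap variation.

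**The case against.** The case for leaving the plan alone has four parts.

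- **The size rests on an unknown.** Nothing in the SAP says that the FSM gap varies between schools. At SD 0.1 the excess error is 0.4 points, and it exceeds 8% only at SD 0.3, three-quarters of the whole school-intercept SD. Restricting the sample to each school's lowest attainers and adjusting for EYFSP may compress the gap. This stands: the size is conditional, and modest at the low end.
- **The FSM effect is a different matter from the interaction.** A reader might infer that the interval for the effect among FSM pupils is also usually too narrow. The documents do not support that. It depends on an intercept-slope correlation that the SAP does not give, and under Table 3's common ICC most of the distortion goes. With a negative correlation the interval can be too wide. This stands.
- **The analysis is exploratory.** The SAP ties no decision to a 5% interaction test. This lowers the priority but does not make the interval correct.
- **The interval method is not fully stated.** The SAP promises a CI that allows for clustering, but does not say how `eefanalytics` forms it. So one cannot claim that the package certainly gives the narrow interval, or that the SAP contradicts itself. The only clustering term that the SAP specifies is still the school intercept.

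**Conclusion.** The point holds for the interaction. As specified, its standard error is too small whenever the FSM gap varies between schools: by about 2%, 6% and 13% at assumed gap SDs of 0.1, 0.2 and 0.3, with error of about 5.4%, 6.5% and 8.4%. This is almost independent of the intercept-slope correlation. For the FSM-specific effect no direction can be asserted.

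Two further inferences should be avoided. The primary treatment estimate is not affected, because that model has no FSM term. The FSM MDES of 0.231 is not shown to be wrong, because it reproduces and refers to FSM pupils alone.

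The sizes rest on the Table 3 inputs, a fitted spread of FSM counts and the assumed gap SDs. Because the gap SD is unknown, the variance method should not depend on its being zero. This is a cheap improvement, not a flaw in the main result.

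**What to change.** In Subgroup analyses, keep the point estimates from Equation (1) with FSM and arm by FSM added. State that the standard errors and 95% CIs of both the interaction and the FSM-specific effect (treatment coefficient plus interaction) use school-clustered robust variance. A school-level random FSM slope with free covariance with the intercept is an acceptable alternative. If `eefanalytics` does not accept either, form the CI from the mixed model and divide by the same total SD as for the other effect sizes.

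The cost is a sentence or two in the SAP and a little extra coding, with no new data and no change to the primary analysis. The interaction interval would be about 6% wider if the gap SD is 0.2 and 13% wider if it is 0.3. In simulation, robust variance cost nothing when the gap was constant.
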